This group is a variation of Group 3 of this study. We have designed a new component, "SmartBase", which takes the place of the 3D-printed SmartBone. The SmartBase is a metal base with adjustable metal tabs that support each of IRI legs. In the 3D modeling software, an impact detection function is used to place the IRI tool on the computer model of the patient's glenoid, and the appropriate metal leg is chosen for each slot of the IRI so that the IRI is in the correct position to place the guidepin in the position dictated by the pre-operative plan. The computer software also calculates the height from the tip of the IRI to the point of contact on the computer model of the patient's glenoid for each of the legs. These distances are included in the pre-operative plan provided to the surgeon. In the operating room, the metal tabs of the SmartBase are adjusted to the proper height for each of the corresponding legs of the IRI. The surgeon then uses the IRI to drill the guidepin in the correct position and orientation into the patient's glenoid.

This method has been shown to be equivalent to the IRI group in pre-clinical testing. The rationale for testing this methodology in the current clinical trial is that the SmartBase does not require fabrication of a sterile SmartBone, which will provide a much faster delivery of the patient-specific instrument.

In all enrolled cases the surgeon will have full control to define the optimal position of the guide pin and the final implant. The surgeon can default to standard of care technology in any case in which the IRI or RTI technology cannot be used or results in guide pin position that, in his best medical opinion, is not consistent with the pre-operative plan. Therefore, the surgeon is in full control of all intra-operative decision making and execution of the procedure.

Measurement of Implant Position

Post-operatively we will obtain a CT scan with metal artifact reduction technology within the first few weeks after surgery and will generally obtain this scan prior to discharge from the hospital. A second CT scan will be obtained at two years after surgery. We have used these methods of 3D CT imaging to determine implant position in several prior studies. We have defined the accuracy of these measurements using first generation techniques to be within 1 millimeter and 3 degrees. We anticipate that the accuracy of these second generation imaging techniques will be improved from our earlier work.

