Thus, to reach 20 in each group, randomization envelopes will be created by the statistician, [name] (QHS), that have 12, 13, 13, 10 and 20 in Groups 1-5, respectively. The change in the odds of being assigned to a particular group will change from 25% previously, to 15 to 19% in Groups 1-4, and to 29% in Group 5. They will receive all pre-operative testing, intra-operative care, including all implants and post-operative care that is standard of care and specific to the surgeon and patient decisions for care. The only change for this clinical trial will be the type of surgical instruments used to place the glenoid guide pin, retention of the humeral head for bone quality analysis, placement of the beads and post-operative CT scanning. In all cases the surgeon is able and allowed to use their own surgical judgment to place the guide pin, prepare the bone and place the desired implant. In all cases, the surgeon can use any and all of the standard instruments or guides provided by the implant manufacturer as the surgeon would use if the patient were not enrolled in the study. If the surgeon chooses not to use the IRI or RTI technique then this would be noted as a deviation in plan, the reasons would be recorded and the patient would be excluded from the study without post-operative imaging and their pre-

operative and intra-operative data would be analyzed for the purpose of understanding the reasons for failure of the RTI technology to provide assistance for refinement of the technology.

Detailed Study Design:

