Post-operatively, all patients will receive a CT with MAR and RSA (if chosen) within 3 weeks of surgery. This will be a CT Scan performed with the patients arm by the side in a supine position using metal artifact reduction techniques. In addition patients will receive a second CT scan RSA imaging, provided they originally got RSA, performed 2 to 3 years (\pm 2 months) after surgery. The second CT scan will be performed with MAR techniques and with the patient in the arm by the side position again using metal artifact reduction techniques. We have shown that in a small number of patients the glenoid component can shift in position within the first 3-6 months after surgery making the first CT Scan more accurate for implant position. The images obtained from the post-operative CT scans are placed back into the surgical software and the 3D reconstruction of the post-operative

scapula with the implants is compared to the pre-operative plan. Using measurement tools within the software, developed at Cleveland Clinic, we will compare the position of the actual glenoid component placed in the patient with the desired position specified by the pre-operative plan. The use and validation of these imaging methods to precisely measure implant position has been performed at the Cleveland Clinic in a prior IRB approved studies (IRBs 10-582, 12-997 and 13-652).

Pre-operatively, the high resolution quantitative CT will measure volumetric bone mineral density and the trabecular network of the glenoid. When available, this will be applied to the pre-operative CT for those patients at Main Campus. Patients who have their pre-operative CT completed at non-Main Campus facilities will have the standard of care pre-operative CT. This will be done at the same visit for the standard of care pre-operative CT. Micro CT imaging, which creates a 3D reconstruction of the fine bone structure, in addition to microarchitecture analysis and mechanical testing, will allow assessment of the bone tissue taken from the bone core sample. Between the preoperative imaging and the bone tissue analysis, we will have data to properly determine the quality of the bone stock surrounding the implant. Further correlating this with RSA and 3D CT imaging of implant movement, we can fully develop the cause and effect of bone quality on glenoid component loosening.

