For the experimental group, the cannulated IRIS instrument designed for glenoid pin placement is placed over the guide wire that is contained within the sterile SmartBone and the legs of the instrument are adjusted to record the relationship (location and trajectory) of the guide pin in relation to the patient specific glenoid anatomy. This is done at the time of surgery to properly mimic the desired pin placement. The location of each leg of the IRI is marked on the SmartBone with a surgical pen. The instrument is then removed from the SmartBone model. The SmartBone model is visually compared by the surgeon to the exposed bone surface to ensure that the two match for shape and size. Any adjustments to the surgical site may be done by the surgeon to optimize the match between the model and the exposed glenoid surface. The marks placed by the surgeon on the model are then transferred to the patient bone using a surgical marker or bovie. These marks are in a general location as determined by the surgeon and assist in the placement of the IRI. The IRI is placed onto the patient bone surface in the same manner as it was placed on the SmartBone model and a guide pin provided by the manufacturer is placed into the desired position. The surgeon then removes the IRI and compares by visual inspection the location and trajectory of the guide pin in relation to the patient's bone surface and that within the SmartBones model. Any adjustments in guide pin position can be performed by the surgeon based upon surgical judgment. The surgeon can make any change needed and use any means or instrument that would otherwise be used for standard of care surgery to place the guide pin in any position that the surgeon believed to be best for the patient. If the pin is changed without the use of the IRI then the patient will be excluded from this study and the reasons for failure of the IRI technology to provide accurate pin placement based upon the surgeon's sole determination of accuracy will be recorded and later analyzed as a failure to treat. These patients will not receive post-operative CT scans as we would not be able to use the data within any one group as defined by this study. After placement of the guide pin the remainder of the procedure is completed in the same manner for both groups, using the implant manufacturer's equipment

RTI technology:

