Using the Smartbone surrogate model, the surgeon visually compares the exposed glenoid surface to the Smartbone model to ensure that the two match for size and shape. Any adjustments to the surgical site may be

done by the surgeon to optimize the match between the model and the exposed glenoid surface. Prior to molding the bone cement, bone wax is wiped onto the model to ensure proper release of the cement mold. The surgeon will then mold bone cement around the pin in the Smartbone, capturing the trajectory of the pin and the unique contours of the glenoid rim. A small pin sleeve is inserted over the pin to be embedded within the cement model. Once the bone cement has cured, it is removed from the model and placed onto the patient's glenoid surface. The bone morphology captured in the mold aligns the mold to the patient's anatomy. When the surgeon feels that the model has good fit of the glenoid surface, he may continue with pin placement. After placement of the guide pin, the RTI mold is removed and the remainder of the procedure is completed using the implant manufacturer's equipment and standard surgical protocols. Any adjustments in guide pin position can be performed by the surgeon based upon surgical judgment. The surgeon can make any change needed and use any means or instrument that would otherwise be used for standard of care surgery to place the guide pin in any position that the surgeon believed to be best for the patient. If the pin is changed without the use of the RTI then the patient will be excluded from this study and the reasons for failure of the RTI technology to provide accurate pin placement based upon the surgeon's sole determination of accuracy will be recorded and later analyzed as a failure to treat. These patients will not receive post-operative CT Scans as we would not be able to use the data.

SmartBase technology:

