All analyses will be done using R software (version 3.0.0, Vienna, Austria). A significance level of 5% will be used for all testing.

Data Sheets

Clinical data collected pre- and post-operatively will be passive and active range of motion, manual muscle strength testing and shoulder functional scores, and co-morbidities, all of which are standard of care. Post-operative data will be collected at two years (\pm 2 months) after surgery. We will collect at the time of surgery the implant used, the time for surgical care glenoid exposure to end of pin placement. The implant used, the surgical instruments used and any comments from the surgeon as to the ease of use and accuracy of the instruments. Verbatim comments will be solicited and recorded by a research assistant attending all surgical procedures.

Pre-operative imaging data will include: glenoid version and inclination, estimated pre -morbid inclination, version and depth of glenoid bone loss using the glenoid vault model, preferred implant type inclination and version.

Post-operative implant placement to desired location will be defined for the location of the center peg of the implant in the superior/inferior (SI), anterior/posterior (AP) and medial/lateral (ML) dimension in millimeters and the trajectory of the center peg vs plan in version and inclination. The location of the implant in relation to the joint line as measured by the glenoid vault model will be measured in millimeters. Back side contact of the implant to the bone will be measured as a surface area in direct contact with the bone and any lucent lines around the implant pegs will be measured. Peg perforation and the location of the peg perforation will be recorded. The tantalum beads within each implant will be measured for translational or rotational movement.

Changes in implant position from post-operative CT scan (CT 1) vs the first post-operative CT scan (CT 2) will be correlated with back side seating, implant type, medialization of the joint line and peg perforation and severity of the post-operative pathology.

Study data will be collected and managed using REDCap (Research Electronic Data Capture). Tracking data will be stored in an Excel spreadsheet, which will exist only on password-protected computers or on restricted-access CCF servers. Only study personnel will have access to the data.

Adverse Events and Data Monitoring Committee (DMC):

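### Deliberate guide-pin changes are recorded and removed only when tied to the IRI or RTI; in Groups 1 and 2 the same decision stays in the analysis as unflagged deviation from plan

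*Combined protocol and SAP*

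**What the plan says.** Discretion is universal. The text under Group 5 in the section on glenoid instrumentation and planning states: "In all enrolled cases the surgeon will have full control to define the optimal position of the guide pin and the final implant". Patient Enrollment repeats it: "In all cases the surgeon is able and allowed to use their own surgical judgment to place the guide pin".

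The yardstick is fixed. Under Detailed Study Design, "we will compare the position of the actual glenoid component placed in the patient with the desired position specified by the pre-operative plan". Data Analysis then compares average deviation from plan between groups by mixed-effects ANOVA. No text updates the plan after an intended intra-operative change, and none treats such a change separately.

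The recording rule is narrower than the discretion. Patient Enrollment says "If the surgeon chooses not to use the IRI or RTI technique then this would be noted as a deviation in plan", and continues that "the reasons would be recorded and the patient would be excluded from the study without post-operative imaging". The IRI section adds "If the pin is changed without the use of the IRI then the patient will be excluded from this study", and the RTI section "If the pin is changed without the use of the RTI then the patient will be excluded from this study". Both require the reasons to be recorded and withhold the post-operative CT.

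Data Sheets lists, for all cases, the preferred implant type before surgery, the implant and instruments used, and surgeon comments on how easy and accurate the instruments were. It adds: "Verbatim comments will be solicited and recorded by a research assistant attending all surgical procedures".

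**The concern.** The trial asks how closely each set of instruments delivers an approved plan. A surgeon who sees the exposed bone and decides on a different pin position has not shown that the instruments are inaccurate. If that happens in a guided group without the guide, the protocol names it, asks why, and takes the patient out. If it happens in Group 1 or Group 2, the full distance from plan enters the group mean and nothing marks it as intended.

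The IRI section justifies its exclusion on the ground that such data could not be used within any defined group. That reasoning applies equally to an override with standard instruments, but the rule is not extended to them. Followed as written, the plan gives a one-sided comparison whose natural direction favours the new instruments. The size of the tilt cannot be recovered afterwards, because intent on pin position in Groups 1 and 2 was never captured.

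**Working it through.** The documents state no SD, effect size, power or override rate, so there is no figure of the plan's own to reproduce. The check is textual first, then illustrative.

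**1. What happens to each kind of change, by group**

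| Event | Groups 1–2 | Groups 3–4 | Group 5 |
|---|---|---|---|
| Guide not used | Cannot occur: no IRI or RTI | Reason recorded, excluded, no CT | Same, if read as an IRI group |
| Pin deliberately changed without the guide | Kept and scored; no record required | Reason recorded, excluded, no CT | Same, if read as an IRI group |
| Pin changed with the guide | Not applicable | Kept and scored; no record required | Same |
| Implant or bone preparation changed after the pin | Kept and scored; intent not recorded | Same | Same |

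Only the first two rows treat the groups differently. Group 2 has a SmartBone but no IRI or RTI, so setting the SmartBone aside triggers nothing. The SmartBase section has no exclusion rule of its own. Group 5 falls under the rule only because it uses the IRI.

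**2. Illustrative shift in the Group 1 or 2 mean**

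Assumed inputs: version error normal with mean 0 and SD 5 degrees; a fraction f of 5–15% deliberately moved by D of 8–10 degrees; outcome taken as absolute deviation.

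For an error with mean D and SD s, E|X| = s√(2/π)·exp(−D²/2s²) + D·[1 − 2Φ(−D/s)].

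- D = 0: 5 × 0.798 = 3.99
- D = 8: 3.99 × 0.278 + 8 × 0.890 = 8.23
- D = 10: 3.99 × 0.135 + 10 × 0.954 = 10.09 (before rounding of the factors)

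Increase = f × (E|X| at D − 3.99):

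- f = 5%: 0.05 × 4.24 = 0.21, to 0.05 × 6.10 = 0.30 degrees
- f = 15%: 0.15 × 4.24 = 0.64, to 0.15 × 6.10 = 0.91 degrees

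Relative to 3.99 this is 5% to 23%.

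**3. Effect on the overall test**

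Simulation: 10,000 runs, five groups of 20, no true difference in execution error, one-way ANOVA at 5% on absolute deviation, surgeon effect ignored. Overrides are scored in Groups 1–2, and removed and replaced in Groups 3–5. False-positive rates:

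| Override rate | 1 SD move | 2 SD move | 3 SD move |
|---|---|---|---|
| 0% | 5% | 5% | 5% |
| 5% | 5% | 6% | 8% |
| 10% | 5% | 9% | 15% |
| 20% | 6% | 21% | 45% |
| 30% | 9% | 42% | 77% |

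With the same handling in every group the rate stays between 4.5% and 5.4%. The two calculations agree: at 10% and 2 SD the simulated excess is 0.123 SD, or 0.6 degrees at SD 5, and the formula gives 0.10 × 6.10 = 0.61. Moves of 8–10 degrees are 1.6–2 SD, so the 1 and 2 SD columns at 5–20% bracket step 2. The simulation removes every override from Groups 3–5, which is the full extent of the asymmetry.

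**The case against.** Several points on the other side are sound.

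- *Implant changes.* A reader might infer that a changed implant also penalises only Groups 1 and 2. The documents do not support that. The recording rules concern use of the guide and the pin. After the pin, the guided groups also proceed with the manufacturer's equipment, so implant and bone-preparation changes are unlogged and scored in all five groups. They add noise but no shown asymmetry, and a changed implant type can be found from the preferred and used implant in Data Sheets.
- *Comments are already solicited in every case.* True, but their stated subject is the ease and accuracy of the instruments. An intended change of position would surface only by chance, and no analysis rule uses it.
- *The exclusion is the main driver, not the missing flag.* This stands. If every patient were scanned and kept, overrides would count everywhere, and a difference would need unequal override rates, which the documents do not show. Without the flag, though, no one could say whether the rates were unequal.
- *The size is assumed.* This stands. Surgeons approve their own plans, so frequent large overrides are not evident. Data Analysis also does not say whether deviations are signed or absolute; signed changes in opposite directions could cancel.
- *Override is part of standard care.* It could be treated so, but then it should count in the guided groups too.

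**Conclusion.** The point holds for guide-pin position. The plan gives the same freedom to all groups and the same fixed reference to all imaged patients, but identifies and removes overrides only where the IRI or RTI is involved. This can tilt the comparison towards Groups 3 and 4, and towards Group 5 if it is read as an IRI group.

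A reader might go further and infer that the benefit of the guides is inflated by a known or large amount. The documents do not support that. The shift of 0.2–0.9 degrees rests on an assumed SD, override rate and move size and on an absolute-error outcome. If overrides are rare or near 1 SD, the overall test is barely affected. Nor can one infer that every deliberate change in the guided groups is identified, since those made with the guide or after the pin are not. What is established is a one-sided rule with a likely direction, and a size the trial has no means of estimating.

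**What to change.** Apply one rule to all five groups.

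1. On the existing intra-operative sheet, before closure, the research assistant already attending records whether the final pin position or implant was deliberately changed from the approved plan (yes/no), the reason, and whether the change followed a guide problem.
2. Keep all randomised patients in the main comparison, including those whose guide was abandoned or overridden. This reverses the present exclusion and means giving those patients the post-operative CT that Detailed Study Design already plans for every patient.
3. Add one sensitivity analysis that treats deliberate changes not caused by a guide problem identically in every group, for example by omitting them everywhere. Report their frequency by group.
4. Name Group 5 explicitly in the rule.

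The cost is one data item, the planned CT for patients now excluded, and one sensitivity analysis; no extra staff are needed. The weakness is that the flag rests on an unblinded surgeon's report, so a miss could be relabelled as intent. That is why the analysis using it should be supportive and not the main one. What the surgeon may do in theatre does not change.

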To extend the studies of implant position of the IRI study (IRB# 12-997) and the RTI study (IRB# 13-652), RSA imaging will be obtained from up to 20 subjects at these same time points. RSA imaging uses bi-planar fluoroscopic imaging within a calibration grid and image software to define implant position. This technology has been a standard for precise implant position for the last 20 years and has been used in thousands of patients. RSA imaging uses metallic markers placed in the implant and in the surrounding bones. The beads implanted in the bone and implant do not move, and are then used as markers to define the location of the implant to the bone and the bones to one another. The accuracy of RSA measurement has been reported to be +/- 0.006mm in translation and 0.5 degrees in rotation. For RSA measurements, a minimum of three 1mm radiopaque tantalum beads into an implant and at least three beads into the surrounding bone when using the RSA system.

Placement of three beads into the implant will also improve the ability of the post-operative 3D CT imaging to define the location of the implant and will be an improvement over our first generation technology. A metal wire is placed in the center peg of the implant by the manufacturer of the implant to better identify the implant

and its location on post-operative imaging. The three additional beads that we place in the implant will add accuracy to the post-operative imaging.

The risk of the bead becoming loose has been shown to be very small and there is no adverse effects related to bead movement or loosening. We have placed these metallic markers in the glenoid implant (three beads) and in the bone (4-5 beads) in 66 patients to date under the ongoing IRI and RTI studies. We have not had any problems with bead placement or any adverse events during or after surgery.

RSA and 3D CT measurements will be correlated and compared. Our goal is to define the accuracy of second generation 3D CT scanning when compared to a gold standard of RSA measurements.

Bone Quality Measurements

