To assess bone quality and its effect on glenoid component loosening, we will take humeral head bone samples from all patients. These bone samples will be assessed by microCT to measure trabecular bone volume and connectivity as well as by mechanical testing. These data will be correlated with the trabecular bone volume of the glenoid defined by the pre-operative CT scans. In addition all bone quality measurements will be correlated with CT scan imaging of the glenoid at the time of surgery and at two year follow up.

In order to acquire consistent information on bone quality across the patients, a custom-made calibration phantom object will be located between the CT bed and the patient. The phantom object consists of three cylindrical rods, each with a known density of hydroxyapatite (0, 500, and 1,000 mgHA/cm³) embedded in a soft foam block. The grey-level of pixel from the rods will be used to calibrate the Hounsfield units and the corresponding bone density using custom-written software.

Patient Enrollment

The proposed clinical trial will randomly enroll patients indicated for standard of care anatomic total shoulder arthroplasty into one of the four treatment groups. Our goal is to have 20 subjects in each treatment group. To accomplish this goal, we will enroll up to 120 subjects to control for subject withdrawal after enrollment. To enroll at least 20 patients into each group, including Group 5 (SmartBase), new randomization envelopes will be generated that start at number 34. The distribution of patients into Groups 1 – 4 at the time that Group 5 was begun is:

Group 1: 8
Group 2: 7
Group 3: 7
Group 4: 10

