The IRI legs are placed virtually (manually) on a virtual SmartBone using an impact detection function in the 3D modeling software. From there the height of each IRI leg is measured and correlated to a number on the SmartBase. The SmartBase has hashes in 1/2 mm increments. The surgeon is then given a pre-operative plan that includes virtual photos of the IRI placement, the IRI leg lengths and numbers of each SmartBase height as calculated. Intra-operatively the IRI is assembled as normal and placed onto the SmartBase after each adjustable tab has been set to the appropriate height for each leg. The IRI is then used as normal.

Inclusion/Exclusion Criteria:

To be eligible for inclusion, a primary anatomic total shoulder arthroplasty must be indicated for the patient.

Outcome Measures:

By comparing computer generated pre-operative plan to post-operative component placement, we will be looking at three outcomes. First, we will compare the overall difference in component placement between the four treatment groups: SOC instrumentation, SOC instrumentation with SmartBone, intelligent reusable instrument with metal instead of plastic legs, and real time instrumentation. Secondly, we will compare the placement between the technologies within and between surgeons. All of the surgeons have extensive experience with anatomic total shoulder arthroplasty. Two of the surgeons have extensive experience with the pre-operative planning and the IRI and RTI technology. Thirdly, we will evaluate the difference in implant position between technologies based on severity of pathology. The quality of the bone core samples will be correlated to the possible loosening of the implants.

Sample Size:

We intend to have approximately 20 subjects in each of the 4 treatment groups. We expect to randomize up to 120 subjects to achieve 20-25 subjects in each treatment group.

Data Analysis

Average deviations from plan for the four treatment groups will be compared using mixed-effects ANOVA methods. Random effects will be included to account for correlation between observations introduced as a consequence of multiple observations of deviation being taken on a particular surgeon. If significant differences are found, multiple comparisons based on the ANOVA model will be made to compare each pair of groups, and will use Holm's step-down procedure to control the family-wise error rate of the tests.

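### The second CT is set at two years in two sections and at 2 to 3 years in another, and the analyses of implant migration make no allowance for the unequal interval

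*Combined protocol and SAP*

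**What the plan says.** On the timing of the second scan:

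- Measurement of Implant Position: "A second CT scan will be obtained at two years after surgery". No tolerance is given. For RSA, the same section says "RSA imaging will be obtained from up to 20 subjects at these same time points".
- Bone Quality Measurements: bone quality is to be correlated with "CT scan imaging of the glenoid at the time of surgery and at two year follow up".
- Detailed Study Design: the second CT, with RSA for those who had it the first time, is to be "performed 2 to 3 years" after surgery, with a tolerance of 2 months either way.
- Data Sheets: "Post-operative data will be collected at two years", again plus or minus 2 months, in a paragraph that opens on range of motion, strength and functional scores.
- Adverse Events and Data Monitoring Committee: the term of the study is put at roughly 1 year from surgery.

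For the first scan, Detailed Study Design says "all patients will receive a CT with MAR and RSA (if chosen) within 3 weeks of surgery".

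On the analysis, Data Sheets says that changes in position between CT 1 and CT 2 "will be correlated with back side seating, implant type, medialization of the joint line and peg perforation and severity of the post-operative pathology". Bone Quality Measurements and Detailed Study Design add correlations of bone quality with later imaging and implant movement. The only model in Data Analysis is for the group comparison: "Average deviations from plan for the four treatment groups will be compared using mixed-effects ANOVA methods", with random effects for surgeon.

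**The concern.** A coordinator who follows Detailed Study Design could properly book, at three years or slightly later, a scan that two other sections place at two years. Patients would then contribute changes in position measured over quite different intervals, and the planned correlations would treat those changes as alike.

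If components keep moving, part of the spread in the change is simply spread in follow-up. At the least that is noise, which weakens real associations. If scan timing happens to be related to surgeon, pathology or implant type, it is also confounding. At stake is the stated secondary aim of explaining glenoid loosening by bone quality, for which Detailed Study Design claims it can establish cause and effect.

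**Working it through.** The documents give no figure for migration or for its variation, so there is no plan figure to reproduce. The check is date arithmetic followed by an illustration.

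**Reading of the labels.** I take CT 1 as the early scan and CT 2 as the late one. The Data Sheets sentence attaches the words for the first post-operative scan to CT 2, which cannot be meant if a change over time is intended.

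**Window for the second scan, in months from surgery**

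| Source | Stated timing | Range |
|---|---|---|
| Measurement of Implant Position; Bone Quality Measurements | two years, no tolerance | 24 |
| Detailed Study Design | 2 to 3 years ± 2 months | 24 − 2 = 22 to 36 + 2 = 38 |
| Data Sheets (only if it covers imaging) | two years ± 2 months | 24 − 2 = 22 to 24 + 2 = 26 |
| Adverse events section | study term about 1 year | about 12; reaches none of the above |

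Under Detailed Study Design the window is 38 − 22 = 16 months wide, and its ends stand in the ratio 38/22 = 1.73. If the Data Sheets window did apply to CT, the figures would be 26 − 22 = 4 months and 26/22 = 1.18.

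**Interval between scans.** The first CT may be up to 3 weeks after surgery: 21 days / 30.4375 = 0.69 month. The shortest interval is 22 − 0.69 = 21.3 months and the longest is 38.

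**What the interval could do to the measured change.** This rests on assumed patterns of migration that are not in the documents. The first scan is taken as done at surgery.

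- Constant rate: the change at 38 months relative to 22 months is 38/22 = 1.73.
- Exponential levelling-off with time constant τ: ratio = (1 − e^(−38/τ)) / (1 − e^(−22/τ)).

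| τ (months) | Ratio, 38 v 22 months |
|---|---|
| 3 | 1.00 |
| 6 | 1.02 |
| 12 | 1.14 |
| 24 | 1.32 |

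If all movement were over by 6 months, the ratio would be exactly 1.

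**Allowance for time in the analysis.** The factors listed for correlation with the change are seating, implant type, joint-line medialization, peg perforation and severity of pathology, with bone quality added elsewhere. Time since surgery is not among them. No section defines a migration rate, a time term or a rule for late scans, and the list of data to be collected does not name scan dates.

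**The case against.** The strongest reply is that the interval may hardly matter. The only evidence in the protocol on the timing of movement, in Detailed Study Design, is that in a small number of patients the component can shift within the first 3 to 6 months. If movement then stops, a scan at 22 months and one at 38 months show the same thing. This stands as a limit on the size of the problem. It does not remove it: the protocol does not say that movement stops, and a late scan to study loosening makes most sense if later change is possible.

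Several stronger readings are tempting, and the documents do not support them:

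- *That the main result is biased.* The outcomes compare the plan with post-operative placement, and Detailed Study Design calls the first CT the more accurate one for implant position. The protocol does not say outright which scan is used, but the early one appears to be meant.
- *That CT timing is given as two years in three places, so that a 4-month window conflicts with a 16-month one.* Only two sections name CT at two years. The window of ± 2 months around two years comes from a paragraph that reads as clinical data.
- *That clinical scores will be set against a scan taken a year later.* No section plans to relate motion, strength or functional scores to the second CT.
- *That Group 5, which started later, will be scanned at a different time.* The window runs from each patient's own surgery, and Groups 1 to 4 go on enrolling alongside Group 5 (12, 13, 13 and 10 further envelopes against 20). The planned migration analyses are also not group comparisons.

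**Conclusion.** The point holds, as a minor one. The sections contradict each other on when the second CT and RSA take place, the widest reading allows 22 to 38 months after surgery, and the stated study term of about 1 year fits none of the timings. No analysis of change between the scans accounts for the interval. The consequence is confined to the secondary migration and loosening correlations.

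Its size cannot be fixed from the documents. A reader might take 1.73 as the bias, but it is the ratio of the two ends of the window. It becomes a ratio of migration only if movement is constant over time, and it then applies only to the two most extreme patients. With early levelling-off the ratio is 1.00 to 1.02. Confounding is possible but not shown: nothing in the documents says that scan timing will be related to any of the factors studied.

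**What to change.** 1. Reconcile Measurement of Implant Position (CT and RSA), Bone Quality Measurements, Detailed Study Design and the study term in the adverse events section to one stated window for the second CT and RSA. Which timing is right is for the investigators to settle.
2. State whether the two-year window in Data Sheets covers imaging or only clinical data, and correct the CT 1 and CT 2 labels there.
3. Record the dates of surgery and of both post-operative scans.
4. Include the actual interval from CT 1 to CT 2 as a covariate in the analyses of change between the scans, by regression or partial correlation. For RSA, with up to 20 subjects, do this at least as a sensitivity analysis.

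The cost is a wording correction, some date fields and one degree of freedom in each model. No patient or scan is added. If migration does level off early, the covariate will explain little and do little harm.
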